### **6.3.6 Administration of ACTIMMUNE**

The first SC injection of ACTIMMUNE will be administered by the patient or their parent/guardian under the guidance of a medical assistant, nurse or physician. Subsequent injections will be administered independently by the patients or their parent/guardian.

Titration dosing will be used to reduce the severity of ACTIMMUNE related flu-like symptoms as described by Devane et al (27). Body surface area (BSA) will be calculated by the Mosteller method (28).

For subjects with BSA >0.5 m^2:

- 10 mcg/m^2 SC three times weekly during week 1
- 20 mcg/m^2 SC three times weekly during week 2

- 30 mcg/m^2 SC three times weekly during week 3
- 40 mcg/m^2 SC three times weekly during week 4
- 50 mcg/m^2 SC three times weekly during week 5
- 60 mcg/m^2 SC three times weekly during week 6
- 70 mcg/m^2 SC three times weekly during week 7
- 80 mcg/m^2 SC three times weekly during week 8
- 90 mcg/m^2 SC three times weekly during week 9
- 100 mcg/m^2 SC three times weekly during week 10 and the remainder of the study if tolerated. ACTIMMUNE may be reduced on a case-by-case basis to manage subsequent drug-related AEs (e.g. flu-like reactions, elevated liver function tests or any drug-related Grade 2 or higher AE).

For subjects with BSA  $\leq 0.5$  m^2:

- 0.3 mcg/kg SC three times weekly during week 1
- 0.6 mcg/kg SC three times weekly during week 2
- 0.9 mcg/kg SC three times weekly during week 3
- 1.2 mcg/kg SC three times weekly during week 4
- 1.5 mcg/kg SC three times weekly during week 5
- 1.8 mcg/kg SC three times weekly during week 6
- 2.1 mcg/kg SC three times weekly during week 7
- 2.4 mcg/kg SC three times weekly during week 8
- 2.7 mcg/kg SC three times weekly during week 9
- 3.0 mcg/kg SC three times weekly during week 10 and the remainder of the study if tolerated. ACTIMMUNE may be reduced on a case-by-case basis to manage subsequent drug-related AEs (e.g. flu-like reactions, elevated liver function tests or any drug-related Grade 2 or higher AE).

Over-the-counter and prescription medications can be used to treat flu-like reaction side effects per the study physician's discretion. Possible treatment options for the flu-like reaction include

administering ACTIMMUNE 1-2 hours prior to bedtime, acetaminophen administration 30 minutes prior to injection, and/or prednisone 5 mg po in morning on day of injection (titrate up to a maximum of 60 mg po day of injection – based on dosing for inflammatory disorder of musculoskeletal system; adjunct).

#### **6.4 Unscheduled Study Visits**

Additional visits will be scheduled with study physicians or local physicians as needed throughout the study period to address concerning signs or symptoms reported by subjects.

Subjects may withdraw voluntarily from the study at any time. If a subject opts to discontinue, attempts will be made to schedule and conduct an Early Termination visit for medical assessment.

If a subject withdraws after an AE, they will be followed until resolution of the issue or until their condition is stable. In the event that a subject becomes pregnant, then discontinuation, reporting, and follow-up procedures outlined in Section 8.3.4 will be followed.

#### **6.5 Study Protocol Compliance / Treatment Adherence**

Adherence to treatment will be evaluated by querying subjects every month either at scheduled study visits or by phone.

#### **6.6 Deviations from the Clinical Protocol**

When a deviation from the protocol is necessary for an individual subject, the Investigator must contact the study PI prior to the deviation (unless the deviation is safety related). The subject may continue in the study by mutual agreement of the Sponsor and the Investigator. A description of the deviation from the protocol and justification must be recorded on the Protocol Deviation Form.

#### **6.7 Protocol Amendments After Study Initiation**

Should changes in the study plan or protocol become necessary in the course of the study, those specific changes will be discussed and agreed upon by the Investigators and appropriate IRB approval obtained before the changes are implemented. All changes must be documented as protocol amendments.

#### **6.8 Subject Withdrawal**

Subjects will be encouraged to complete the study; however, they may voluntarily withdraw at any time. If a subject is withdrawn prior to study completion, attempts will be made to schedule and conduct an Early Termination visit for medical assessment. If a subject cannot be contacted after 5 telephone calls and 3 letters, they will be considered lost to follow-up.

Subjects who discontinue study medication (e.g., due to non-compliance, side effects, etc.) will be asked to remain in the study for follow-up per the study schedule to preserve the ability to perform a

safety analysis. If a subject or their legal guardian (as applicable) withdraws consent to participate in the study, attempts will be made to obtain permission to record survival and adverse event (malignancy, hospitalization for infection) data at the 12-month study point.

As long as the link between the sample ID code and the subject name is maintained by the clinical study site, it will be possible for subjects to ask that their samples be withdrawn. However, we anticipate this link will be destroyed at some point in the future, after which withdrawal of samples will not be possible. In addition, once DNA samples have been provided to collaborators, we cannot guarantee that all samples will be able to be tracked down.

## **6.9 Subject Compensation**

Travel reimbursement up to \$1,500 will be provided for each of the Screening, Baseline, Month 3, Month 6, and Month 12 study visits. This reimbursement can be applied to flights for subject or subject and 1 parent/guardian, gas, hotel (to be chosen and reserved by study coordinator for the number of nights required to complete study visit[s]), and/or food (up to \$150/visit). Receipts will need to be provided to study coordinator for reimbursement. Subjects will also receive \$50 at Screening, Baseline, Month 3, Month 6, and Month 12 study visits as compensation for their time and inconvenience.

## **6.10 Subject Compensation for Research Related Injury**

If a subject is injured as a result of taking part in this study they will receive medical treatment, however this care will be billed to their insurance in the usual manner and will not necessarily be free of charge to the subject.

## **6.11 Sharing Results with Subjects**

All results obtained in this study are for research only. No results will be shared with the subjects other than those needed to care for the subject during study participation (e.g. abnormal lab test). When results are shared with the subject, they will be discussed in person or by telephone.

# **7 Data Collection and Analysis**

## **7.1 Subject Population(s) for Analysis**

- Treatment-compliant population: Any subject who received at least 85% of prescribed doses and attended all scheduled study visits.
- Safety population: All subjects who receive any amount of treatment.

## 7.2 Statistical Methods

### 7.2.1 Sample size Determination

This is a pilot study to obtain data for a larger, definitive clinical trial. The sample size of 10 was determined based on feasibility estimates including potential screening failures

### 7.2.2 Statistical Analysis

Descriptive analyses of baseline characteristics and outcomes will include means and standard deviations for continuous variables and frequencies for categorical variables. Confidence intervals and P-values will be based on a t-distribution. Statistical significance will be considered as  $p < 0.05$ . The primary endpoint and safety analyses will be primarily descriptive reporting the number and percentage of compliance and AEs. The secondary endpoints for hematologic function, immune function, and bone mineral density will be evaluated by paired t-tests or chi-squared to evaluate change from baseline to 12 months. Secondary endpoints related to in vitro osteoclast assays will be descriptive.

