## Study Summary

Title	Open-label Phase 1/2 Study with a Single Arm of Interferon Gamma-1b Treatment of Osteopetrosis
Study Sponsor	[name], MS Assistant Professor, Pediatric Endocrinology David Geffen School of Medicine Los Angeles Biomedical Research Institute at Harbor-UCLA Medical Center
Principal Investigator (PI)	[name], MS Assistant Professor, Pediatric Endocrinology David Geffen School of Medicine Los Angeles Biomedical Research Institute at Harbor-UCLA Medical Center
Study Design	multi-center open-label phase 1/2 clinical trial
Study Duration	Subjects will participate in the study for 1 year. It is expected that enrollment will be completed in 18 months and the last subject will complete the protocol 2.5 years after study initiation.
Study Center(s)	
 
1. LABioMed at Harbor-UCLA [name] [name]
 
2. University of Minnesota [name] [name]
 

Study Objectives	
 
1. To determine the feasibility and tolerability of interferon gamma-1b treatment in patients with intermediate osteopetrosis.
 
2. To determine the safety and efficacy of interferon gamma-1b in patients with intermediate osteopetrosis.
 

Study Endpoints	
Primary Endpoint: The primary objective of this pilot study is to determine the feasibility and tolerability of interferon gamma-1b treatment for 1 year in patients with intermediate osteopetrosis. Specifically, i) the ability to enroll patients, and ii) continued treatment throughout the 1-year observational period.
 
Secondary Endpoints: The secondary objectives of this study will focus on change in immunologic and hematologic function, bone mineral density and osteoclast function, physical function and quality of life.

Number of Subjects	10
Main Inclusion Criteria	
 
• Intermediate Osteopetrosis, defined as: 
 
○ Anemia, or
 
○ Neutropenia, or
 
○ <math>\geq 1</math> serious infection over prior year defined as requiring hospitalization and/or IV antibiotics, or
 
○ History of impaired bone healing
 
 
 
• Age <math>> 1</math> year
 

Duration of Observation	1 year

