## 4 Study Objectives / Hypotheses

### 4.1 Primary Hypothesis

The primary hypothesis to be tested is:

That treatment with IFN- $\gamma$ 1b will be feasible and tolerable to patients with intermediate osteopetrosis.

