## 5.2 Anticipated Duration of the Clinical Investigation

Each subject will be enrolled in the study for 12 months. It is expected that 15 patients will be screened over 18 months to enroll 10 participants, with the final subject completing study participation 2.5 years after study initiation. The final study report will be completed approximately 3 years after study initiation. If the study is terminated prior to completion, a closeout report will be filed with the Institutional Review Board (IRB) within 3 months of study termination.

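### The primary endpoint is enrolment plus a year of continued treatment, but its planned analysis is compliance, reported alongside AEs: enrolment has no planned analysis, and compliance is undefined in 7.2.2 and need not mean that treatment continued

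*Combined protocol and SAP*

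**What the plan says.** The Study Endpoints row of the Study Summary sets feasibility and tolerability over 1 year as the primary matter and then makes it concrete: "Specifically, i) the ability to enroll patients, and ii) continued treatment throughout the 1-year observational period". Section 4.1 introduces feasibility and tolerability with "The primary hypothesis to be tested is".

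The analysis is one sentence in 7.2.2, repeated in the Statistical Methods row of the Study Summary: "The primary endpoint and safety analyses will be primarily descriptive reporting the number and percentage of compliance and AEs". Neither place defines compliance, gives a denominator or mentions enrolment. Section 7.2.2 also bases confidence intervals on a t-distribution.

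The only numerical definition of compliance is that of the treatment-compliant population in 7.1: "Any subject who received at least 85% of prescribed doses and attended all scheduled study visits". Section 7.1 also defines a safety population of everyone who receives any treatment.

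On subjects who stop the drug, 6.8 says: "Subjects who discontinue study medication (e.g., due to non-compliance, side effects, etc.) will be asked to remain in the study for follow-up".

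Enrolment figures appear outside section 7: 5.2 expects 15 screened and 10 enrolled over 18 months, and item 2 of the monitoring plan (Appendix A) lists screened, enrolled, screen-failure, dropout and completion counts for the periodic report.

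**The concern.** A primary analysis should report the primary endpoint. Here one of the two components, enrolment, has no planned statistic. The other, continued treatment, is represented by a word that 7.2.2 leaves undefined and that, on the only definition available, measures something else: the share of doses taken combined with visit attendance.

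Section 7.2.1 says this pilot is meant to supply data for a larger, definitive trial. Recruitment yield and the proportion of patients who stay on interferon gamma-1b for a year are the figures that such a trial would need. Under the plan as written, the first need not be reported as a result, and the second could be reported as a percentage that includes subjects who stopped and leaves out subjects who continued.

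**Working it through.** **Reproducing the plan's own figure.** N = 10 rests on feasibility, so there is no power or precision formula to reproduce. The planning figures agree with each other: 18 months of enrolment + 12 months of follow-up = 30 months = 2.5 years, as 5.2 states.

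**Endpoint against analysis.**

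| Primary endpoint component (Study Summary) | Planned analysis in section 7 |
|---|---|
| Ability to enrol | None |
| Continued treatment for 1 year | Number and percentage of compliance, undefined in 7.2.2 |

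AEs stand in the same sentence, but it covers safety as well, so they can be read as the safety half.

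**Does compliance equal continued treatment?** This step assumes that compliance in 7.2.2 means the 85% rule in 7.1.

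Inputs: three injections a week (6.3.6: "SC three times weekly during week 10 and the remainder of the study if tolerated"); 12 months per subject (5.2: "Each subject will be enrolled in the study for 12 months"), taken as 52 weeks; threshold 85% (7.1).

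- Planned doses: 3 × 52 = 156.
- Doses needed: 0.85 × 156 = 132.6, so 133. Doses that can be missed: 156 − 133 = 23.
- Earliest permanent stop with no earlier misses: 133 / 3 = 44.3 weeks, which is 52 − 44.3 = 7.7 weeks before the end.
- Range for the ±1 week visit window: 51 weeks gives 153 doses, 131 needed, stop at week 43.7; 53 weeks gives 159 doses, 136 needed, stop at week 45.3.

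A subject who stops at that point, stays on the visit schedule as 6.8 asks and attends month 12 is compliant, although treatment did not continue.

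The reverse also occurs. A subject still on drug at month 12 who took 80% of doses (0.80 × 156 = 124.8, below 133), or who missed the month 6 visit, is non-compliant although treatment continued. Month 6 is the example because 5.4.8 and 6.3.1 withdraw a subject who misses month 3.

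**The denominator.** Section 7.1 does not say whether prescribed doses keep accruing after a stop. On a full-year denominator, a stop at month 3 gives 39/156 = 25% and at month 6 gives 78/156 = 50%, both non-compliant. If the denominator ends at discontinuation, a stop at any time can give up to 100% of doses, so an earlier stopper who attends every visit could also be compliant.

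**Size at N = 10.** Each subject classified differently moves the percentage by 1/10 = 10 points. As an illustration only, suppose two subjects stop in the last 7 weeks and all else is perfect:

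- compliant: 10/10, exact (Clopper-Pearson) 95% interval 69% to 100%;
- continued through month 12: 8/10, exact 95% interval 44% to 97%.

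A t-based interval for 10/10 has zero width, because the standard deviation of ten identical values is 0.

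**Enrolment, if it were analysed and the plan were met.** 10/15 = 67% of those screened (exact 95% interval 38% to 88%), and 10/18 = 0.56 enrolled per month.

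**The case against.** The strongest reply is that this is a ten-subject descriptive pilot and that compliance is a loose label for staying on treatment. Section 7.2.2 does not cite the 85% rule, 7.1 offers that rule only to define an analysis population, and the protocol uses the word more broadly in 6.5 and 5.4.8. This stands as a limit: the late-stopper example is conditional on the 7.1 definition. It does not rescue the plan, because on any other reading the main primary statistic has no definition.

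The late-stopper case is also narrow. Section 5.4.8 ends participation for certain Grade 3 or higher events, and 8.4 item 6 withdraws subjects who cannot safely tolerate the study. Such subjects would miss later visits and fail the 7.1 rule. What remains, on a full-year denominator, is a subject who stops in roughly the last 7 to 8 weeks, missed few or no doses before, is not withdrawn, and attends every visit. That stands.

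Enrolment is not ignored either: the monitoring report tabulates it, and 8.4.2 lists unsatisfactory enrolment as a reason to terminate. So the gap lies in the analysis plan and not in data capture.

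A reader might go further and infer that early stoppers would be scored as primary successes, that true dropouts would be credited, or that the two measures would lead to opposite feasibility decisions. The documents do not support this. They set no success criterion or go/no-go rule, a dropout who misses visits cannot meet the 7.1 rule, and nothing suggests that two of ten subjects would stop in the late window.

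**Conclusion.** The point holds as a mismatch between endpoint and analysis. Enrolment, one of the two primary components, has no planned primary analysis; this follows from the text without any assumption. Continued treatment is summarised by compliance, which is undefined in 7.2.2 and, on the only numerical definition in the protocol, can depart from continued treatment in both directions.

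The effect is on the reported primary percentage, by 10 points for each discordant subject. The week-44 figure rests on 52 weeks of dosing, a full-year denominator, no earlier misses and the 7.1 definition. If prescribed doses end at discontinuation, the window widens to a stop at any time. The change should be made, because following the present wording would leave part of the primary endpoint unreported.

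**What to change.** Replace the primary-endpoint sentence in 7.2.2 and its copy in the Statistical Methods row of the Study Summary together, so that the two stay consistent. State two primary analyses:

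1. Enrolment: numbers screened, eligible and enrolled over 18 months, set against the 15 and 10 expected in 5.2.
2. Continued treatment: number and proportion of the safety population who continued study drug through month 12, with an exact binomial 95% interval in place of a t-based one. A permanent stop before month 12 counts as not continued. Temporary interruptions and their length are reported separately, so that a long gap followed by a restart stays visible.

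Report the 85% compliance figure as supportive, with the prescribed-dose denominator fixed as the full planned year, and report AEs under safety. In 4.1, replace the tested hypothesis with a descriptive objective to estimate items 1 and 2.

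Cost: wording in three places and one CRF item. The enrolment counts are already collected for monitoring. The protocol does not state that a last-dose date is recorded; 6.5 provides only for monthly adherence queries, so the date should be added to the CRF as part of that query. Sample size, visits and treatment do not change. The drawback is that the reported primary percentage may be lower when a subject stops late.

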Statistical Methods	Descriptive analyses of baseline characteristics and outcomes will include means and standard deviations for continuous variables and frequencies for categorical variables. Confidence intervals and P-values will be based on a t-distribution. Statistical significance will be considered as $p < 0.05$ . The primary endpoint and safety analyses will be primarily descriptive reporting the number and percentage of compliance and AEs. The secondary endpoints for hematologic function, immune function, bone mineral density, physical function and quality of life will be evaluated by paired t-tests or chi-squared to evaluate change from baseline to 12 months. Secondary endpoints related to in vitro osteoclast assays will be descriptive.

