### 4.2 Secondary Hypotheses

The secondary hypotheses are:

1. Compared to baseline, treatment with IFN- $\gamma$ 1b will result in:
  - a. Decreased tibial volumetric bone mineral density (**vBMD**) and estimated bone strength measured by peripheral quantitative computed tomography (**pQCT**);
  - b. Decreased total body and lumbar spine areal BMD (**aBMD**) by dual-energy x-ray absorptiometry (**DXA**);
  - c. Increased levels of markers of bone remodeling (see Table 1);
  - d. Increased osteoclast activity by *in vitro* testing;
  - e. Increased white blood cell (**WBC**) and platelet counts in patients that have lower than expected blood counts at baseline.
  - f. Increased height standard deviation score (**SDS**) for participants <18 years with open growth plates;
  - g. Decreased inflammation measured by erythrocyte sedimentation rate (**ESR**);

[figure not shown]
- h. Decreased pain score (based on prior 4 weeks);
  - i. Increased physical function score (based on prior 4 weeks); and
2. Compared to the 12 months prior to study entry (based on medical record review or subject recollection), treatment with IFN- $\gamma$ 1b over 12 months will result in:
  - a. Decreased number of hospitalizations for infection;
  - b. Decreased number of days treated with antibiotics;
  - c. Beneficial change in WBC and platelet counts in patients who have lower than expected blood counts at baseline;
  - d. Beneficial change in ESR;
  - e. Increased height SDS for participants  $<18$  years with open growth plates; and
3. Patients will not develop neutralizing antibodies.

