#### **Subjects who are not yet adults (infants, children, teenagers)**

- Subjects in the United States are considered minors if they are 17 years or younger, with the exception of Alabama (18 years), Nebraska (18 years or upon marriage), and Mississippi (20 years)
- Parental permission will be obtained from:
  - One parent even if the other parent is alive, known, competent, reasonably available, and shares legal responsibility for the care and custody of the child.

- Parental or guardian (as defined by DHHS and FDA regulations) consent will be obtained. A guardian must provide written documentation of the legal ability to consent to for the child's participation in research. A copy of this documentation will be kept with the consent document.
- Assent will be obtained from all minor subjects aged 7 to 17 years.
- Assent will be documented with their signature on the assent form.

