### 6.3.3 Medical examination and Anthropometrics

A trained pediatric provider will perform a physical examination at each visit. Tanner staging of pubertal development, including breast and pubic hair development in girls, and testicular size and pubic hair development in boys will be performed at baseline, 6, and 12 months for participants < 18 years of age or < Tanner stage 5. Height will be measured 3 times standing without shoes. The average of 3 measurements by the same observer using identical technique with a wall-mounted stadiometer will be recorded. Each subject will be repositioned between each measurement. Height standard deviation score (SDS) will be calculated based on the

National Center for Health Statistics 2000 data as provided by the Center for Disease Control. Weight to be measured standing, once with subject in light clothing or dressing gown with shoes removed. These measurements will be used to calculate body mass index (BMI) as weight (kg) divided by height ( $m^2$ ).

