#### **6.3.4 Radiographic assessments**

##### **6.3.4.1 Dual energy x-ray absorptiometry (DXA)**

DXA (Hologic [Harbor] and GE [Minnesota]) measurements will be obtained for total body less head, L1-L4 lumbar spine, and for subjects  $\geq 18$  years of age femoral neck and total hip as well. Standardized procedures for participant positioning and data processing will be used for all scans. Standardization of data from different machines is done by standardized phantom scanning protocols.

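### Section 7.2.2 tests 12-month BMD change in a single arm that admits children, without an age- and sex-referenced scale for areal BMD under 18 (minor point)

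*Combined protocol and SAP*

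**What the plan says.** - **Hypothesis.** Section 4.2, item 1b, expects, compared with baseline, "Decreased total body and lumbar spine areal BMD".
- **Test.** Section 7.2.2 states that "bone mineral density will be evaluated by paired t-tests or chi-squared to evaluate change from baseline to 12 months". The Study Summary has the same approach: "bone mineral density, physical function and quality of life will be evaluated by paired t-tests". Neither says on what scale the BMD change is measured. For a continuous BMD value the paired t-test is the relevant option.
- **Design.** The title is "Open-label Phase 1/2 Study with a Single Arm of Interferon Gamma-1b Treatment of Osteopetrosis", so there is no concurrent control.
- **Population.** Section 5.4.5 admits patients older than 1 year, with assent from age 7 to 17. Section 6.1 has a consent subsection for "Subjects who are not yet adults (infants, children, teenagers".
- **DXA.** Section 6.3.4.1 says "measurements will be obtained for total body less head, L1-L4 lumbar spine, and for subjects" of 18 and over the hip regions are added. The age limit therefore applies to the hip regions only; the two regions in hypothesis 1b are scanned in minors as well. The one standardisation named is between scanners: "Standardization of data from different machines is done by standardized phantom scanning protocols".
- **Height, by contrast.** In section 6.3.3, "Height standard deviation score (SDS) will be calculated based on the" national reference data that it names. The CHQ-PF50 and SF-36 summary scores also use population norms (sections 6.3.5.1 and 6.3.5.2). No BMD Z-score, BMD reference set or height adjustment of BMD appears anywhere.

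**The concern.** In a single-arm before-and-after comparison, anything that changes over 12 months is part of the estimate. In an adult, growth adds nothing. In a child, if areal BMD rises with growth, the raw change is drug effect plus growth, and the two have opposite signs under hypothesis 1b. The plan expects growing participants: it has a height hypothesis for those under 18 with open growth plates (section 4.2) and Tanner staging (section 6.3.3). It references height for age but not BMD.

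The pooled result would then depend on how many growing participants happen to enrol. A null or positive BMD result at p < 0.05 could be misread as absence of a drug effect. Section 7.2.1 says that the pilot is meant to supply data for a larger, definitive trial, and a mean change of unknown composition is poor planning input.

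**Working it through.** **No plan figure to reproduce.** The documents give no power, effect size, SD of BMD change, share of children or yearly BMD gain. The sample size of 10 rests on feasibility (sections 5.4.1 and 7.2.1). The figures below only show the trade-off.

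**Inputs from the documents:** n = 10; 12-month change; significance at p < 0.05 (sidedness not stated, two-sided taken).

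**Inputs assumed:** the outcome is percent change; SD 4 points; true drug effect -5% in everyone; 5 of the 10 growing; growth g = 2, 4 or 6% a year.

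**Step 1. No growth.** One-sample t-test, 9 df, critical value 2.262. Noncentrality = (5/4) × √10 = 3.95. The noncentral t gives a 94% chance of a significant decrease.

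**Step 2. Growth present, change not referenced.** Expected mean change = -5 + (5/10) × g. This is -4.0, -3.0 and -2.0 for g = 2, 4 and 6. The spread also widens, because growing and non-growing participants now have different means. Chances are by simulation.

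**Step 3. Growth removed by a reference.** Growth is replaced by any error left by the reference (its bias) plus extra spread of SD 3 points in the five growing participants. The referenced changes are put through the same t-test solely to size gain against cost; this is not proposed as an analysis.

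| Scenario (5 of 10 growing) | Chance of a significant decrease, effect -5% |
|---|---|
| No growth | 94% |
| Not referenced, growth 2 / 4 / 6% | 78 / 46 / 15% |
| Referenced, no bias | 87% |
| Referenced, under-corrects by 1 / 2 points | 79 / 68% |

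**Step 4. No drug effect (nominal 2.5% on each side).**

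| Scenario (5 of 10 growing) | Significant increase | Significant decrease |
|---|---|---|
| Not referenced, growth 2 / 4 / 6% | about 10 / 22 / 35% | 0.3% or less |
| Referenced, no bias | 2.5% | 2.5% |
| Referenced, over-corrects by 1 / 2 / 3 points | below 2.5% | 5 / 8 / 12% |

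**Step 5. Is over-correction plausible here?** Section 2.1 describes generalised high bone mass. Suppose a child gains the same absolute BMD as the reference child but starts at r times the reference level. The child's percent gain is then g/r, and subtracting g over-corrects by g - g/r. With g = 4, r = 1.5 gives 4 - 2.67 = 1.33 points and r = 2 gives 4 - 2 = 2.0 points. The size on a Z-score scale would differ and cannot be worked out from the documents.

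**Sensitivity to the mix.** With only 2 growing at 2% a year, the unreferenced test has 89% power and the unbiased referenced one 91%, so almost nothing is gained. With 7 growing, the unreferenced figures are 70 / 27 / 4% and the unbiased referenced one 85%.

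**The case against.** The case for leaving the plan alone has four parts.

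- **Weight.** Areal BMD is one secondary hypothesis of a 10-patient pilot whose primary endpoint is feasibility and tolerability, analysed descriptively. No power is claimed. This stands, and it is why the point is minor.
- **Direction.** The unreferenced test errs against the hypothesis. A reader might infer that the plan risks a false claim of benefit. The documents do not support that: under the growth assumption, a false decrease appears in 0.3% or less of trials in step 4.
- **The remedy can do harm.** Referencing swaps an error against the hypothesis for one that may favour it, and step 5 shows why that is plausible in these patients. A reader might conclude that a pooled test of referenced change should replace the raw one. That does not follow: no passage calls for such a scale, and a reference that is off by 1 to 3 points would yield a false decrease in 5 to 12%. Referenced change should be shown, not tested.
- **Modest gain.** If the reference under-corrects by 1 point, 79% is hardly better than the unreferenced 78% at 2% growth. The gain is clear only with faster growth or more growing participants.

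Three further readings go too far. The plan does not commit to raw units; it is silent on scale. The argument concerns areal BMD and is not carried over here to the pQCT volumetric measures of hypothesis 1a. Nor would referencing show that a change is due to the drug: the trial is uncontrolled, nearly all other therapies are permitted (section 5.4.4), and low vitamin D is treated, with calcium where needed (section 6.3.2).

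**Conclusion.** The point holds as a minor one. The omission can be verified: minors are eligible, the two regions in hypothesis 1b are scanned in them, BMD change is tested in one arm, and nothing references areal BMD for age and sex although height is referenced. The consequence rests on one assumption that the documents do not quantify, namely that areal BMD rises with growth over 12 months. If so, the unreferenced change tends to hide the hypothesised decrease or to show a rise. In the illustration with five growing participants, power drops from 94% to between 78% and 15%, according to growth; every input there except n and the 0.05 level is assumed.

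The primary endpoint is not affected. With few or slowly growing participants the effect is small, and with adults only it is nil.

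**What to change.** In section 7.2.2, and in the matching Study Summary text:

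1. State the scale of the BMD change.
2. For participants under 18, add that 12-month change in areal BMD (total body less head, lumbar spine) will also be given as change in an age- and sex-referenced score, for example a Z-score. Fix the reference for each site's machine, and any height adjustment, before analysis.
3. Report the referenced change descriptively, as an estimate with confidence interval, beside the raw change. Show under-18 and adult changes separately, without subgroup tests.
4. State that the pooled raw test will not be read as evidence for or against hypothesis 1b if growing participants are included.
5. Label any decrease seen only after referencing as dependent on the reference. Report minors with no suitable reference on the raw scale only.

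**Cost.** Analysis-plan wording and a reference lookup. Age, sex, height and DXA are already obtained, so no new visit or scan is needed. A reference adds its own error and may over-correct in patients with high bone mass, which is why raw change stays beside it. Whether a reference covers children from just over age 1 on both makes of scanner cannot be judged from the documents.
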